- *Are physically dependent on alcohol, opioids or benzodiazepines such that immediate medical detoxification is necessary for safety purposes* (individuals demonstrating significant withdrawal symptoms would be eligible for re-screening following brief medical detoxification, which is arranged by MCCA or SATU staff at triage).

2. Rationale for sample choice. We are proposing relatively few exclusions that parallel our

completed trials of CBT4CBT^{119, 123} in recruiting a broad range of individuals whose primary substance use problem is alcohol (those with low levels of drug use will be eligible providing they do not meet current disorder criteria). *The inclusion criterion regarding level of drinking is consistent with NIAAA definitions of risky/heavy drinking^{167, 168} and comparable to prior randomized trials for establishing efficacy of cognitive behavioral treatments^{3, 28, 169}. We will exclude those initiating an alcohol pharmacotherapy to limit potential confounds, as well as exclude individuals experiencing significant alcohol withdrawal symptoms in need of medical detoxification for safety reasons.*

C.2.c. Procedures

1. Initial screening by Research Coordinator: All new MCCA or SATU patients will be invited to participate in the protocol at the time of their initial clinic appointment. See below for detailed description.

2. Urn randomization: To increase the likelihood that treatment groups are balanced with respect to demographic variables (gender, race, education) as well as likely prognostic variables (severity of alcohol dependence, level of familiarity with and access to computers) participants will be assigned to treatment conditions through urn randomization^{173, 174}, using a Microsoft Access program we have implemented successfully in multiple trials^{138, 142, 171, 175, 176}.

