C.2.f. Data Management and Analyses

The system of data management will include a combination of scannable forms (Teleforms), direct entry interface (Access), and a relational database (SQL Server) within a closed, secure network, allowing data to flow in a continuous cycle of collection, processing, error checking, and correction on a real-time basis while the study is ongoing. Outlined below is the general strategy for data analyses which will address each of our specific aims. Preparatory analyses will include evaluation of baseline equivalence of groups on demographic and prognostic variables, comparability of rates of data availability and treatment exposure across conditions^{239, 240}, *as well as consideration for the potential contribution of assessment reactivity*^{241, 242}. Data analyses will be conducted on the intention to treat sample, and we will attempt to follow all participants regardless of their retention in the treatment arm of the trial^{179, 180}.

Aim 1 - Evaluation of treatment effects:

The principal strategy for assessing the efficacy of the study treatments on outcome will be random effects regression models for continuously measured *primary* (e.g., percentage of days abstinent - PDA) and secondary (e.g., percentage of heavy drinking days, quality of life, etc.) outcomes. Our research group has used these methods to evaluate main and interaction effects, with appropriate covariates (e.g., retention, compliance with treatment) in multiple previous trials^{121, 138, 142, 171, 172}. *We will include treatment utilization data during the follow-up period as a covariate in analyses evaluating treatment effects through follow-up.*

Analysis of treatment effects at post-treatment and follow-up will include the following contrasts:

- **H1a:** *Main effect for CBT on PDA by month during treatment:* Clinician-CBT and CBT4CBT>TAU.
- **H1b:** *Main effect for CBT on PDA by month through follow-up:* Clinician-CBT and CBT4CBT>TAU.

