The procedures for SAE reporting include written documentation using the clinical notes related to the adverse event and specific forms detailing the event with a sign-off by all appropriate supervisory personnel. Communication of recommendations and decisions from all parties (DSMB, Yale Human Investigations Committee, and MCCA or SATU Administration) are made back to the investigator in a timely manner. We will report all protocol amendments or changes in the informed consent form to NIAAA as well as any temporary or permanent suspension of patient accrual.

- d. For multi-site studies for which the Yale PI serves as the lead investigator: **N/A**
 - i. How will adverse events and unanticipated problems involving risks to subjects or others be reported, reviewed and managed?
 - ii. What provisions are in place for management of interim results?

iii. What will the multi-site process be for protocol modifications?

11. Statistical Considerations: Describe the statistical analyses that support the study design.

Aim 1 - Evaluation of treatment effects:

The principal strategy for assessing the efficacy of the study treatments on outcome will be random effects regression models for continuously measured primary (e.g., percentage of days abstinent - PDA) and secondary (e.g., percentage of heavy drinking days, quality of life, etc.) outcomes. Our research group has used these methods to evaluate main and interaction effects, with appropriate covariates (e.g., retention, compliance with treatment) in multiple previous trials^{121, 138, 142, 171, 172}. We will include treatment utilization data during the follow-up period as a covariate in analyses evaluating treatment effects through follow-up.

Analysis of treatment effects at post-treatment and follow-up will include the following contrasts:

- **H1a:** *Main effect for CBT on PDA by month during treatment:* Clinician-CBT and CBT4CBT>TAU.
- **H1b:** *Main effect for CBT on PDA by month through follow-up:* Clinician-CBT and CBT4CBT>TAU.

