Adequacy of sample size: *H1a* – Using conventional effect size estimates, we determined that our proposed sample size of 60 per condition would be sufficient for detecting a small-medium effect ($d=.35$) of treatment on PDA using a random effects regression model (2 groups, PDA by month, 3 data points, ICC=.6, alpha=.05, beta=.80). *H1b* – The proposed sample is sufficient to detect a medium effect ($d=.50$) through the follow-up period with a random effect regression model (2 groups, PDA by month, 7 data points, ICC=.6, alpha=.05, beta=.80). These effect sizes are conservative, based on estimates from completed studies of CBT4CBT^{119, 122}.

Power calculations	Power	Estimated effect size	# of datapoints	Sample size per cell
H1a: (Clinician CBT + CBT4CBT stand-alone) v TAU, main effect for active treatment	.80	.35	3	60
H1b : (Clinician CBT + CBT4CBT stand-alone) v TAU, main effect for follow up	.80	.50	7	60

Aim 2 – Evaluation of skills acquisition as mediator of CBT effects:

Latent growth curve modeling will be the principal strategy for evaluating mediation using Mplus version 7²⁵¹. The product of coefficients method^{18, 19} will be used to determine the mediating effects of skills acquisition during the treatment period on PDA during follow-up. We will be using the 6-month period following treatment as our alcohol use outcome in this model to support the temporal relation criterion⁶⁴, as well as to evaluate the delayed emergence of CBT's effect on alcohol use¹³⁹. This model will test:

- **H2a:** *Effect of CBT on acquisition of skills (a₂ path: X→M):* Clinician-CBT>TAU; CBT4CBT>TAU
- **H2b:** *Effect of change in acquisition of skills on PDA by month during follow-up (b₂ path: M→Y)*

- **H2c:** *Indirect effect of CBT on PDA via change in acquisition of skills ($a_2 * b_2 / se_{a2} * se_{b2}$)*

Adequacy of sample size: Parameter estimates from our initial trial of CBT4CBT that supported coping skills acquisition as a mediator of treatment effects on substance use⁹⁶ were used to estimate effect sizes of treatment condition on PDA via skills acquisition ($a=.26$; $b=.59$). Based on these effect sizes and power estimates for testing mediation derived from a simulation study⁹⁴, we will have adequate power (.80) to detect significant mediating effects with the proposed sample size of 60 per condition.

SECTION VI: RESEARCH INVOLVING DRUGS, BIOLOGICS, RADIOTRACERS, PLACEBOS AND DEVICES

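### The urn balancing factors are not named as covariates in the H1a and H1b models; modest precision may be lost if they are prognostic and the contrast is an averaged main effect

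*Combined protocol and SAP*

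**What the plan says.** **Randomisation.** C.2.c, item 2 (Urn randomization) uses an urn to make it more likely that the arms are "balanced with respect to demographic variables (gender, race, education" and on "likely prognostic variables (severity of alcohol dependence, level of familiarity with and access to computers". That is five factors, counting computer familiarity and access as one.

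**Analysis.** C.2.f (Aim 1) and Section V item 11 (Aim 1) carry the same text: "The principal strategy for assessing the efficacy of the study treatments on outcome will be random effects regression models". The next sentence says the group has used these methods in earlier trials "with appropriate covariates (e.g., retention, compliance with treatment". For the follow-up analysis there is a firm commitment: "We will include treatment utilization data during the follow-up period as a covariate in analyses evaluating treatment effects through follow-up". No urn factor is named in either place.

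**Baseline variables.** Within the Aim 1 plan they appear only in the preparatory analyses of C.2.f, as "evaluation of baseline equivalence of groups on demographic and prognostic variables". Alcohol severity (AUDIT) returns later, but as an exploratory moderator.

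**Contrast and power.** H1a and H1b are both labelled main effects of CBT, with the two CBT arms set together against TAU. The H1a power inputs are "2 groups, PDA by month, 3 data points, ICC=.6, alpha=.05, beta=.80", with 60 per condition and d = .35. H1b uses 7 points and d = .50. The table in item 11 gives power .80 for both.

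**The concern.** The design spends effort balancing five factors and the stated analysis does not use them. In a linear model, a prognostic factor that was balanced at allocation but left out of the model stays in the residual, although the design has already removed part of it from the arm contrast. The reported standard error is then a little larger than the true sampling SD. The reduction in residual variance that adjustment would bring is also lost.

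A second consequence is discretion. With the covariate list open and a baseline comparison planned, the choice of covariates can be made after seeing which factors differ between arms. Naming the factors in advance removes that choice for the variables most likely to be considered.

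**Working it through.** **Inputs.** From item 11: both CBT arms (120) against TAU (60); ICC .6; m = 3 and d = .35 for H1a; m = 7 and d = .50 for H1b; alpha .05. Sidedness is not stated and I take it as two-sided. Assumed: R², the share of variance in a participant's mean PDA explained by the five factors, at .05, .15 and .30.

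**Step 1. The plan's own figure.** SD of a participant's mean = sqrt((1 + (m−1)·ICC)/m).

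- H1a: sqrt(2.2/3) = .8563. SE = .8563 × sqrt(1/60 + 1/120) = .8563 × .1581 = .1354. Power = Φ(.35/.1354 − 1.96) = .734.
- H1b: sqrt(4.6/7) = .8106. SE = .8106 × .1581 = .1282. Power = Φ(.50/.1282 − 1.96) = .974.

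The stated .80 is not reproduced for either. Other readings:

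- 60 v 60 gives .610 (H1a) and .922 (H1b).
- One-sided 120 v 60 gives .826 and .988.
- Change from one baseline month gives .815 for H1a (SD sqrt(.4 × 1.5) = .7746, SE .1225) and .996 for H1b.

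No single reading tried gives .80 for both. The adjusted figures below start from .734 and .974.

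**Step 2. Gain from adjustment, averaged main effect.** SE_adj = SE × sqrt(1 − R²). Equivalent sample size factor = 1/(1 − R²).

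| R² (assumed) | SE ratio | H1a SE | H1a power | H1b SE | H1b power | Equivalent n |
|---|---|---|---|---|---|---|
| 0 | 1.000 | .1354 | .734 | .1282 | .974 | 1.00 |
| .05 | .975 | .1320 | .756 | .1249 | .979 | 1.05 |
| .15 | .922 | .1248 | .801 | .1182 | .988 | 1.18 |
| .30 | .837 | .1133 | .871 | .1072 | .997 | 1.43 |

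**Step 3. Simulation under an urn.** n = 180, three arms, five binary factors, H1a variance as above, 3,000 trials per setting. The urn starts with one ball per arm and adds one for each arm not drawn. Factor prevalences, and the weight on severity (60% of the explained variance), are assumptions.

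| R² | Unadjusted SE / true SD (d = 0) | Type I, unadjusted → adjusted | Adjusted SE | H1a power, unadjusted → adjusted |
|---|---|---|---|---|
| .05 | .1355/.1323 = 1.02 | .048 → .045 | .1334 | .733 → .743 |
| .15 | .1353/.1312 = 1.03 | .046 → .049 | .1260 | .721 → .777 |
| .30 | .1355/.1286 = 1.05 | .043 → .052 | .1144 | .734 → .863 |

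- At d = .35 the SE/SD ratios are .1353/.1344 = 1.01, .1354/.1320 = 1.03 and .1355/.1293 = 1.05.
- Simulation error is about sqrt(.05 × .95/3000) = .004 on type I error and 1/sqrt(2 × 3000) = 1.3% on the SD. At R² = .05 the overstatement is therefore not clearly separable from none.
- A second simulation (12,000 trials per setting, a different urn rule, participant-mean SD scaled to 1, R² .05/.10/.20) gave .158 against true SDs of .156, .155 and .153. That is 1.3%, 1.9% and 3.3%, with type I error .047, .045 and .043.
- The simulated gains are slightly below the formula because the extra terms cost some information.
- The urn-induced overstatement is the smaller part of the drop in SE once R² is not trivial: (.1353 − .1312)/(.1353 − .1260) = 44% at R² = .15, and (.1355 − .1286)/(.1355 − .1144) = 33% at R² = .30. The rest is ordinary covariate adjustment, which would be available without an urn.

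**Step 4. If the test is on change over time.** The 3-point slope SE is sqrt(.4/2) × .1581 = .0707. With the five factors added it is .0715. The random intercept already absorbs anything that shifts a participant's level, so there is no gain unless the factors also predict change.

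**The case against.** **The covariate list is open.** The sentence giving retention and compliance as examples describes earlier trials and is not a closed list. A reader might infer that the H1a/H1b models leave the urn factors out. The documents do not say so; they only fail to name them. This objection stands, and the point is confined to pre-specification.

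**Prognostic strength is not given.** Only severity and computer familiarity/access are called likely prognostic. Gender, race and education are called demographic, and the urn is meant to make balance more likely, not to force it. At R² = .05 the H1a gain is about two power points by formula and one by simulation. This stands, so every size here is conditional on R².

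**The error is on the safe side.** A reader might infer that the primary standard errors are materially wrong or the test invalid. The calculations do not support that: the overstatement is a few per cent, type I error stays at or just below .05, and the estimate is unbiased.

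**H1a may not be an averaged contrast.** Eight weeks of treatment yield two months, so three monthly points plausibly include baseline. The pilot result in C.1.e was a condition-by-time effect, and the change-from-baseline reading brings H1a near .80 (.815). On that reading adjustment gains about nothing. Against this, both hypothesis lists and the power table call the contrasts main effects. The wording favours the averaged reading but does not settle it.

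**Conclusion.** The gap is real and modest. The analysis text does not name the factors used in the randomisation, and the covariates it does name are all measured after randomisation.

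On the averaged two-sided 120 v 60 contrast, and if the factors are prognostic, naming them would raise H1a power from about .73 to between .76 and .87 over an assumed R² of .05 to .30. For H1b the power gain is negligible. The gain shrinks if baseline PDA is already in the model and is about nil for a change or group-by-time test. Validity is not at stake. This is a nearly free improvement, not a defect that threatens the primary conclusion.

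Whether the post-randomisation covariates belong in the treatment-effect models is a separate question and is not decided here.

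**What to change.** Add to the Aim 1 text in C.2.f and in Section V item 11, in words such as: *The H1a and H1b models, and the models for continuous secondary outcomes, include gender, race, education, severity of alcohol dependence and computer familiarity/access as fixed baseline covariates, coded as in the urn program, whatever the baseline comparison shows. No other covariate is chosen on the basis of that comparison.*

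The second sentence is needed because naming five factors does not by itself close the open covariate wording. List the urn categories alongside, since the documents do not give them.

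Cost: two sentences and at least five degrees of freedom out of 180 participants (more if race or education has several categories). No new data are needed, because the urn requires these values before assignment. If H1a proves to be a slope test, the price is about 1% on its standard error (.0715/.0707 = 1.011).

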For HIC Use Only**Date Approved****Human Investigation Committee Signature****This protocol is valid through** _____**SECTION V: RESEARCH PLAN**

1. **Statement of Purpose:** State the scientific aim(s) of the study, or the hypotheses to be tested. Well-controlled randomized clinical trials of computer-assisted therapies are very rare, and there are few that would meet current methodological standards established for traditional evidence-based treatments. We propose to conduct a randomized clinical trial of our web-based version of Computer Based Training in Cognitive Behavioral Therapy (CBT4CBT) to evaluate its effectiveness relative to therapist-delivered cognitive behavioral therapy or standard outpatient counseling with participants with alcohol use disorder. Specific aims are as follows:

Aim 1 – Evaluate the efficacy of CBT4CBT and clinician-delivered CBT relative to standard treatment for reducing alcohol use through an 8-week randomized trial with 6-month follow-up. Our primary hypothesis is that either form of CBT will be more effective than standard treatment at increasing the percentage of days abstinent (PDA)^{2, 3} during treatment (8 weeks) and through the follow-up (6 months), assessed via Timeline FollowBack interviews^{4, 5}. Secondary outcomes will include percentage of heavy drinking days (PHDD)^{6, 7}, urine ethyl glucoronide analysis (EtG)⁸⁻¹⁰, drinking-related consequences^{11, 12}, quality of life¹³, and cost effectiveness¹⁴.

Aim 2 – Evaluate the extent to which CBT's putative mechanisms act as mediator of treatment effect on reducing alcohol use in both forms of CBT relative to standard treatment.

Hypothesized mechanisms include enhanced behavioral, cognitive, and affective control, measured within treatment by indices reflecting acquisition and implementation of targeted skills (behavioral role-play assessment¹⁵, coping strategies inventory^{16, 17}, and measures of homework completion and knowledge of CBT). Latent growth curve modeling will test for mediation using the product of coefficients method^{18, 19}. We hypothesize:

- (a) greater increases in skills acquisition for those assigned to either form of CBT compared to TAU;
- (b) increased acquisition of skills during treatment will be associated with greater PDA during follow-up;
- (c) CBT's effect (in either delivery format) on PDA will be mediated by skills acquisition.

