3. Treatment phase: Study treatments will last 8 weeks. During the treatment phase, all participants will meet weekly virtually either via Zoom and/or phone with research staff for completion of self-report and interview assessments. In all conditions, we will closely monitor participant treatment response and safety via BAC, urine screens which are taken by the clinic on the clinic's usual schedule and assessment of psychiatric status. Although in our experience this is a very rare event in behavioral trials¹⁷⁷, including those of computer-delivered interventions^{110, 119, 122}, participants who show significant deterioration (e.g., significant increases in alcohol use or psychiatric symptoms that cannot be managed within the protocol) will be regarded as symptomatic failures, withdrawn from the treatment arm of the study, and referred for

appropriate treatment (typically a more intensive level of care). See Protection of Human Subjects, below.

4. Termination, post-treatment assessment, and follow-up: At the end of the 8-week treatment period, all participants will be re-interviewed (see Assessments) virtually either via Zoom and/or phone. Access to the CBT4CBT program will be terminated, and *participants in all three conditions will be offered the opportunity to continue in treatment as usual at MCCA or SATU if desired/needed*. Follow-up interviews (using the full post-treatment battery that includes treatment utilization) will be conducted 1, 3, and 6 months after termination virtually either via Zoom and/or phone. We will attempt to follow all participants in our intention-to-treat sample, using strategies that have been successful in our multiple previous studies¹⁷⁸, where our *current rate of follow-up approaches 90-95% across studies*^{149, 179, 180}.

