1. Standard treatment as usual (TAU): Participants randomized to this condition will receive treatment-as-usual at MCCA or SATU. This typically consists of *group counseling delivered by masters-level and certified counselors trained and employed by MCCA or SATU and supervised by MCCA Clinic Director*, [name], or the SATU Clinical Director, [name]. Patients in this and all conditions are offered standard ancillary services, delivery of which is monitored closely throughout the trial (see Assessments).

2. Individual clinician-delivered CBT: Participants assigned to this condition will receive 8 weekly individual sessions of manual guided CBT^{120, 125}, which provides detailed instructions to clinicians regarding the same topic areas covered in CBT4CBT. Clinicians will be trained and supervised using procedures we have developed in multiple previous CBT trials⁵⁰,

^{136, 138} to protect internal validity and treatment integrity. Extensive procedures for clinician selection, training, and supervision should minimize variability in outcome due to ‘therapist effects’¹⁸³, however as noted earlier, some level of clinician variability is expected. The CBT clinicians will be at least masters-level clinicians drawn from MCCA or SATU staff and selected on the basis of audio-taped samples of their work. Following an initial 2-day didactic training, they will each complete at least 3 closely supervised training cases on which they will receive detailed feedback on their fidelity and skill based on ratings of their audio-recorded sessions using our validated therapy process assessment system, the Yale Adherence and Competence Scale (YACS)⁷⁵. Once certified to begin the trial, the CBT clinicians will meet weekly with a CBT supervisor ([name]), which will involve updating of case material, review of audio recordings of each clinicians’ work, and comparison of self-monitoring of CBT implementation with supervisors’ ratings¹⁴⁵ (see Assessments). This technique, used in our previous psychotherapy studies^{143, 145, 184}, is included to assure fidelity to manual guidelines and a consistent high level of adherence and skill throughout the trial. Clinicians will review and make copies of completed homework assignments and will report, after each session, which CBT modules were covered.

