Adequacy of sample size: *H1a* – Using conventional effect size estimates, we determined that our proposed sample size of 60 per condition would be sufficient for detecting a small-medium effect ($d=.35$) of treatment on PDA using a random effects regression model (2 groups, PDA by month, 3 data points, ICC=.6, alpha=.05, beta=.80). *H1b* – The proposed sample is sufficient to detect a medium effect ($d=.50$) through the follow-up period with a random effect regression model (2 groups, PDA by month, 7 data points, ICC=.6, alpha=.05, beta=.80). These effect sizes are conservative, based on estimates from completed studies of CBT4CBT^{119, 122}.

Cost-effectiveness analyses: [name] of American University, an expert in cost analyses, particularly of behavioral therapies with substance using populations²⁴³⁻²⁵⁰, is a member of the Scientific Advisory Board as well as a consultant to [name] NIDA-

supported Psychotherapy Development Center. In this capacity, he directs cost-effectiveness evaluations of Center projects, including all those related to CBT4CBT as well as the proposed study. *He was involved in the design of the Program and Client Costs for Substance Abuse Treatment (PACC-SAT)*^{14, 166}, *the instrument that will be used to assess participants use of a wide variety of physical and mental health services, substance use and legal services utilization. The PACC-SAT covers the 12 months prior to randomization, the full-8 week treatment period, and the entire follow-up period* (See Schedule of Assessments). The general approach used to evaluate cost-effectiveness of the protocol interventions will be to evaluate the relationship between value of resources used in intervention implementation (e.g., *costs associated with the facility, staff, and transportation*) and nonmonetary outcomes produced by the intervention (e.g., *reduction in drinking behavior and drinking consequences, improvement in quality of life*). This will include calculating the total cost for each treatment condition, cost per participant in each condition, as well as outcomes of ‘alcohol-free days’, and comparing the average cost per ‘alcohol-free day’ gained per month across treatment conditions, *using strategies outlined in [name] previous work*^{243, 246, 247, 249, 250}.

Aim 2 – Evaluation of skills acquisition as mediator of CBT effects:

[figure not shown]

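### The follow-up half of the primary hypothesis (H1b) is to be adjusted for treatment received during follow-up, a post-randomisation variable, and no H1b analysis without that covariate is designated

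*Combined protocol and SAP*

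**What the plan says.** Section V.1 (Statement of Purpose, Aim 1) sets the primary hypothesis on PDA over two periods: "during treatment (8 weeks) and through the follow-up (6 months), assessed via Timeline FollowBack interviews". The follow-up part is H1b, listed under Aim 1 in C.2.f and again in Section V.11 as a main effect of CBT, both CBT arms against TAU. For the follow-up analyses both places carry the same unconditional sentence: "We will include treatment utilization data during the follow-up period as a covariate in analyses evaluating treatment effects through follow-up". Neither place, nor any other, designates an H1b analysis without this covariate or says which result governs.

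On where the covariate comes from:

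- C.2.c item 4 places it at the same interviews as follow-up drinking: "Follow-up interviews (using the full post-treatment battery that includes treatment utilization) will be conducted 1, 3, and 6 months after termination".
- The cost-effectiveness part of C.2.f gives the window of the instrument: "The PACC-SAT covers the 12 months prior to randomization, the full-8 week treatment period, and the entire follow-up period".
- C.2.c item 4 describes what happens at week 8. For the computer arm, "Access to the CBT4CBT program will be terminated". For everyone, "participants in all three conditions will be offered the opportunity to continue in treatment as usual at MCCA or SATU if desired/needed".
- C.2.d item 1 says of the control arm: "Participants randomized to this condition will receive treatment-as-usual at MCCA or SATU".

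The form of the covariate (a total or monthly values, which types of care) is not stated.

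**The concern.** Randomisation protects the comparison of arms as long as the model conditions only on things fixed before assignment. Follow-up utilisation is not one of these, and two routes can make it harmful.

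- **Through the outcome.** Continued care is taken up according to wish or need. If CBT lowers drinking and need drives care, the CBT arms will use less care because CBT worked. Adjusting for utilisation then removes part of the effect that H1b is meant to detect.
- **Directly from arm.** What everyone is offered after week 8 is the service the TAU arm already had. For the two CBT arms it is a different one. Uptake could therefore differ by arm whatever the drinking, although the documents do not show that it will.

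The adjusted coefficient is not a clean direct effect of CBT either, if unmeasured factors such as severity or motivation influence both care-seeking and drinking. The follow-up half of the primary hypothesis could then be judged on a number that is not the randomised effect, with no designated result to fall back on.

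**Working it through.** **Inputs from the plan.** H1b sample-size paragraph in C.2.f: d = .50 with "2 groups, PDA by month, 7 data points, ICC=.6, alpha=.05, beta=.80" (the last item read as power .80). The power table in Section V.11 gives 60 per cell and pooled CBT against TAU, so 120 v 60. Sidedness is not stated; two-sided .05 is used.

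**Assumed, because the documents do not give them.** The arm difference in utilisation D (CBT minus TAU, in within-arm SD) and the within-arm slope B of PDA on utilisation (PDA SD per SD). The effect is taken as constant over 7 post-randomisation points, with no missing data.

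**Step 1: the plan's own figure.**

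- Variance of a participant's mean over 7 months: .6 + .4/7 = .657.
- SE = sqrt(.657 × (1/120 + 1/60)) = sqrt(.657 × .025) = .128.
- .50/.128 = 3.90, so power is .974. With 60 v 60 it is .922.

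The stated .80 is not reproduced from these inputs. The plan does not give its formula, so this is not shown to be an error, and the concern does not rest on it. To be fair to the plan's figure, results are also shown with the SE scaled to give .80 at d = .50: .50/2.80 = .178, a factor of 1.39.

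**Step 2: what the covariate does.** In a linear model without interaction:

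- adjusted d = total d − D × B
- SE = sqrt((.657 − B²) × .025 × (1 + D² × 2/9))

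The 2/9 is (120/180) × (60/180).

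**Step 3: utilisation driven only by need.** Let r be the size of the within-arm correlation between utilisation and the participant's PDA level, more drinking going with more care. Then D = −r × .50/sqrt(.6) and B = −r × sqrt(.6), so D × B = r² × .50 and adjusted d = .50 × (1 − r²).

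| r | adjusted d | SE | power | power, SE × 1.39 |
|---|---|---|---|---|
| 0 | .50 | .128 | .97 | .80 |
| .2 | .48 | .126 | .97 | .78 |
| .4 | .42 | .119 | .94 | .72 |
| .6 | .32 | .107 | .85 | .58 |

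With no true effect D = 0, so rejection stays at 5%. Simulation of a random-intercept model (5,000 replicates per setting) gave d of .481/.421/.322 and null rejection of .048/.051/.047. With utilisation entered monthly, d was .480/.419/.318 if it has the same ICC as PDA and .491/.457/.394 if it has no stable person component; null rejection was .047 to .055.

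**Step 4: a separate direct effect of arm on utilisation.** Take B = −.3 or +.3 and D = −.1/−.2/−.3. The shift is .3 × |D|, and the SE is about .120.

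| D | adjusted d, B = −.3 | adjusted d, B = +.3 | null rejection | null rejection, SE × 1.39 |
|---|---|---|---|---|
| −.1 | .47 | .53 | 5.7% | 5.4% |
| −.2 | .44 | .56 | 7.9% | 6.5% |
| −.3 | .41 | .59 | 11.6% | 8.4% |

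The excess rejection favours TAU when B = −.3 and CBT when B = +.3; the directions reverse if D is positive. Simulation (4,000 replicates per setting, SE unscaled) gave null rejection of .059/.076/.111 for B = −.3 and .057/.083/.122 for B = +.3.

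**Step 5: no arm difference.** With D = 0, adjusted d is .50, with no bias.

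**The case against.** The strongest reply is that the harm is conditional. It needs an arm difference in utilisation and an association with PDA, and the documents establish neither. Continued care is offered to all three conditions alike, ancillary services are available in every arm, and the CBT clinicians are themselves clinic staff, so the route from arm to uptake is an inference. In the better-grounded case, where need drives care, the bias is conservative, type I error is unaffected, and power on the recomputed base is still .85 at the most extreme correlation. False rejection on the plan's own power base is lower than the unscaled figures. All of this stands. It limits what can be said about size, but the plan still fixes the covariate before anyone knows whether the arms differ.

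Three further points carry less weight.

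- **Intention to treat.** C.2.f commits to the intention-to-treat sample. That settles who is analysed, not what the model conditions on.
- **The tested term.** The 7 points may include a starting value, and a test of the arm-by-month slope would, with complete data, be unchanged by a person-level utilisation main effect. With 6 points the base barely moves (SE .129, power .972), and both C.2.f and the power table label H1b a main effect.
- **Level of detail.** C.2.f calls itself a general strategy and does not exclude an unadjusted model. But the covariate sentence is a firm commitment made twice, and nothing ranks an unadjusted result above it.

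Adjusting to separate CBT from later care is a legitimate question, but it is a different one from the randomised effect, and the plan does not state it as its target.

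**Conclusion.** The concern holds. As written, the plan can test the follow-up half of its primary hypothesis with a coefficient that is not the randomised effect, and it names no result to rely on instead. Under the assumed ranges a true d of .50 could be reported as anything from .32 (need-driven, r = .6) to .59 (direct effect of .3 SD, slope +.3). False rejection stays near 5% if utilisation is only need-driven. With a direct arm effect of .1 to .3 SD and a slope of .3 it is about 6% to 12%, or 5.4% to 8.4% on the plan's stated power base. These sizes are illustrative: the documents supply neither the arm difference nor the association, and no direction is claimed. The defect in the specification rests on the text alone. It should be corrected before results are seen, because a choice of model made afterwards would be open to challenge.

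**What to change.** In C.2.f and Section V.11:

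- Designate as primary an H1b analysis of the stated contrast (pooled CBT v TAU on monthly PDA over follow-up) that omits follow-up utilisation and adjusts only for pre-randomisation variables, for example the urn factors and baseline PDA. Utilisation before randomisation could also be used.
- If arm-by-month terms are included, define the H1b test as the arm contrast averaged over the follow-up months.
- Report follow-up utilisation by arm.
- Keep the utilisation-adjusted model as a labelled supportive analysis, and define the covariate: total or monthly, and which types of care.

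The cost is wording and a little more analysis; no new data are needed. If the arms truly do not differ in utilisation, omitting it gives up some precision. At a slope of .3 the SE is .128 instead of sqrt((.657 − .09) × .025) = .119, and power .97 instead of .99. Adjustment for baseline PDA may offset this.
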